6. RECRUITMENT METHODS

- *Describe the source of potential subjects*
- *Describe the methods that will be used to identify potential subjects*
- *Describe any materials that will be used to recruit subjects. A copy of any advertisements (flyers, radio scripts, etc.) should be submitted along with the protocol.*
- *If monetary compensation is to be offered, this should be indicated in the protocol*

Aim 1: Adaption Phase

The study team has access to an existing HNC Patient Advisory Board (PAB), which was originally established to aid in the development of the LogPal software program. This group of male and female survivors will be the primary pool of potential participants to achieve Aim 1. If needed, the study team plans to further recruit civilian HNC survivors from Northwell Health as needed to reach complete data goals for Aim 1 (n=15Northwell patients), via phone calls and mailed (email and/or physical) outreach recruitment methods, after first scanning the EMR to identify eligible participants. Additionally, 3 treating HNC providers who treat potential participants that we may approach for participation in this research will be identified to also participate in Aim #1.

Aim 2: Preliminary Evaluation Phase

Research coordinators (RC) at NWH will scan the EMR records facilitated by patient lists generated by our data analyst to identify eligible survivors due for their first standard of care clinical visit after treatment. To supplement these efforts, the study team will use the Oncora and ARIA databases which are used by Northwell's radiation oncology department to create patient cohorts for research purposes. We will use the filtering capabilities within these databases to create lists of eligible HNC survivors within the Northwell system.

Eligibility and permission to approach will be confirmed by the collaborating providers; if the provider does not respond to the request within one week, they will be assented by default. Study staff will contact survivors by phone and via myNorthwell to assess interest in the study. Once eligibility has been established, interested patients will be asked to meet study RCs after the regularly scheduled appointment, and to expect that the visit will be extended by 45-60 minutes. At the end of the clinic visit, the HNC survivor will meet with the RC to give informed consent, record baseline data, and assess drinking patterns with the AUDIT questionnaire and the Time-Line Follow Back (TLFB) alcohol use assessment procedure. Patients will also have the option to elect to consent and complete questionnaires virtually. Randomization will occur after the patient is consented. The RC will access the randomization website and provide alcohol use feedback, plus, if randomized to the intervention arm, register the HNC survivor with the Bottle Cap platform.

Survivors who have consented to participate will be block randomized to either AF or the intervention text messaging arm. This procedure will ensure that even numbers per condition across sites are maintained overall.

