Participants will be compensated up to \$125 for their participation in Aim 1; \$125 will be evenly divided among the total number of interviews needed to compensate participants for their involvement with each interview.

Aim 2

All participants will be initially screened via EMR records for potential eligibility (type of HNC, date(s) of treatment, age, sex, race, and education, etc.). A waiver of authorization for this access has been requested below. Study staff will seek permission to approach potential participants from the HNC survivor's provider before inviting the patient to extend an existing scheduled appointment to participate in the study. At the end of the clinic visit, the HNC survivor will meet with the study staff to obtain informed consent, schedule another time to discuss the study or obtain contact information to send the consent document (i.e., via REDCap or mail). After consent, the coordinator will record baseline data and all assessments. Participants that are found to have clinically significant depression (≥ 16 on the CES-D Iowa short form) will be withdrawn from the study and referred to social work.

Consented participants will then be block-randomized into one of 2 arms:

- i. **Control condition: Assessment and Feedback (AF).** Regardless of drinking level ascertained during the baseline questionnaires, the patient will receive feedback about their reported alcohol consumption from study coordinators (i.e. not through Bottle Cap). Feedback will be provided by study coordinators one time, in person or virtually (depending on how the participant elects to receive their baseline visit), after the baseline measures are completed, and include assessment of alcohol levels and recommending alcohol cessation. The feedback will emphasize that, according to leading medical associations, any consumption of alcohol is not advisable for cancer survivors, as continued

alcohol use is associated with a higher risk of cancer recurrence and reduced quality of life. A sample feedback statement is “one or two drinks might not seem much, but it can increase your chances of cancer recurrence”. Smoking cessation information will also be provided as per usual care. Patients will be urged to stop smoking and referred to a smoking cessation program if so desired. Participants will be asked to complete two follow-up questionnaires, one at 3 and one at 6 months post baseline, during scheduled follow-up visits. No further effort will be required.

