- ii. **Intervention condition.** Survivors recruited from NWH who are randomized into the intervention condition will receive all research activities given in the control condition, plus the HNC-tailored alcohol cessation program. Study staff will register the survivor at the Bottle Cap website and confirm the person’s gender and age. Survivors will receive text messages three times a week, usually during the late afternoon/early evening period, when the risk of alcohol drinking is greatest, for a period of 3 months. Participants will be asked to complete two follow-up questionnaires, one at 3 and one at 6 months post baseline. As with the control condition arm, all study activities will end after 6 months.

All participants will receive up to \$100 compensation at the end of the study for their participation in Aim 2.

It should be noted that participants will have the option of completing all assessments electronically (i.e., via REDCap link), via hard copy (i.e., mailed form), and over the phone or in-person with the CRC/RA. In the event that participants opt to complete the questionnaire via mailed copy, over the phone or in-person, the CRC/RA will input participant responses into REDCap. For this study, all data collected will be coded and entered into REDCap (Research Electronic Data Capture), a vetted HIPAA compliant (Health Insurance Portability and Accountability Act) web-based application that manages research surveys and databases.

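### The plan implies, and does not prevent, that the coordinator opens the allocation before giving the feedback both arms share; giving feedback first would reduce this avoidable risk to the between-arm estimate

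*Combined protocol and SAP*

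**What the plan says.** Section 6 (Recruitment Methods, Aim 2) has the survivor meet the coordinator, give consent, and complete baseline data with the AUDIT and the TLFB. It then states: "Randomization will occur after the patient is consented". The next sentence reads: "The RC will access the randomization website and provide alcohol use feedback, plus, if randomized to the intervention arm, register the HNC survivor".

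Section 11 (Research Procedures, Aim 2) runs through consent, baseline assessments and withdrawal of those who screen positive for depression, and continues: "Consented participants will then be block-randomized into one of 2 arms". Feedback is then described under the control condition: "Regardless of drinking level ascertained during the baseline questionnaires, the patient will receive feedback about their reported alcohol consumption from study coordinators". On delivery: "Feedback will be provided by study coordinators one time, in person or virtually". The same sentence places feedback after the baseline measures but does not place it relative to randomization.

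Section 11 also sets the content: an assessment of the participant's alcohol level, a recommendation to stop, and an emphasis that leading medical bodies advise cancer survivors against any alcohol because of recurrence risk and reduced quality of life. One sample sentence is given. The control arm's other content is not about alcohol: "Smoking cessation information will also be provided as per usual care". Intervention participants "will receive all research activities given in the control condition, plus the HNC-tailored alcohol cessation program".

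Section 12 (Stratification of data) specifies permuted blocks without a block size. It mentions blinding only as something the randomization software can support.

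**The concern.** The trial compares feedback plus texts with feedback alone. The difference isolates the texts only if feedback is delivered in the same way in both arms. Feedback is a single conversation led by a coordinator. A coordinator who already knows the arm might press harder with a survivor who will get nothing more, be briefer with one who will get texts, or put more effort into the arm seen as the active one. The first two would shrink the observed difference and the third would enlarge it.

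The analysis could not put this right. Section 12 plans a 2x2 chi-square test on cessation, and the plan calls for no record of how feedback was delivered. The between-arm difference is also the quantity that Section 12 wants to carry into the design of later trials.

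**Working it through.** **1. Order of steps, section by section.**

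| Step | Section 6 | Section 11 |
|---|---|---|
| Consent | first | first |
| Baseline measures | after consent | after consent |
| Randomization | tied to consent; website access named before feedback | follows baseline and the depression screen |
| Feedback | named after website access, same coordinator | described as arm content; timed only as after baseline |
| Bottle Cap registration | last, intervention arm only | intervention arm only |

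Both sections point to allocation first. Neither states it, and Section 11's timing sentence would also permit feedback first.

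**2. Safeguards.** The themes of the feedback are fixed. There is no full script, recording, checklist or fidelity rating. Oversight is general: staff meetings on protocol adherence (Sections 14 and 27) and coordinators' own monitoring of procedures (Section 15). No section blinds the coordinator.

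**3. How unequal feedback enters the estimate.** Let a_C and a_I be the shifts in control and intervention cessation caused by the coordinator knowing the arm. With Section 12's illustrative rates of 20% and 30%:

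expected difference = (0.30 + a_I) − (0.20 + a_C) = 0.10 + (a_I − a_C).

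The bias is a_I − a_C. It is zero if the arm is unknown during feedback. The documents give neither its size nor its sign.

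**4. The plan's own figure.** Section 12 states 294 per arm for 20% against 30%, two-sided 0.05, 80% power:

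n = [1.960·√(2·0.25·0.75) + 0.8416·√(0.20·0.80 + 0.30·0.70)]² / 0.10² = (1.2002 + 0.5119)² / 0.01 ≈ 293.1, rounded up to 294.

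Allowing for attrition, 294 / 0.85 = 345.9, or 346. Both reproduce.

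**5. Sensitivity of a future trial to this estimate.** This is an illustration, not a measure of the bias. The shifts are assumed and applied to the control arm only, with intervention held at 30% and the same formula used:

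| Observed control cessation | Difference (points) | n per arm implied |
|---|---|---|
| 15% | 15 | 121 |
| 18% | 12 | 198 |
| 20% (no shift) | 10 | 294 |
| 22% | 8 | 471 |
| 25% | 5 | 1,251 |

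**6. Could the pilot reveal such a shift?** With 60 analysed per arm, the 95% half-width of the difference is 1.96·√(0.16/60 + 0.21/60) = 0.154, about 15 points. Shifts of 2 to 5 points would not be visible.

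**7. How far reordering helps.** If blocks are of fixed size 2m with 1:1 allocation, and staff know the size and the past allocations, the share of allocations that can be deduced with certainty is 1/(m + 1). That is 33% for blocks of 4 and 25% for blocks of 6. These block sizes are assumptions, since the plan gives none. If allocations are predictable, a coordinator may know the arm before opening the website.

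**The case against.** The strongest reply is that the text does not establish the sequence. Section 6 joins website access and feedback with a simple conjunction, and Section 11 ties feedback only to baseline. That stands: the order is implied. It does not dispose of the point, because staff follow what is written and nothing written prevents allocation first.

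Second, a reader might infer that the feedback is uncontrolled apart from a sample sentence. The documents do not support this. Section 11 fixes the themes and gives feedback once, whatever the drinking level. This narrows the room for differences without closing it.

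Third, the pilot is not powered for the comparison. Section 12 calls it secondary and exploratory, and feasibility and acceptability are not affected. This stands and limits the stakes. Against it, Sections 4 and 10 name cessation as primary, and Section 12 intends the effect estimate for future trials.

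Fourth, a reader might take an assumed shift of 2 to 5 points and call it 20% to 50% of the planned effect. That does not hold up. The shift has no source. The 10-point difference belongs to an illustrative future trial. Against the 30% difference in H2 (Section 4), read as percentage points, the same shift would be 7% to 17% (2/30 to 5/30).

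Fifth, a reader might infer that reordering removes the bias. It does not, given blocks of unstated size and self-reported outcomes that staff may collect by phone or in person (Section 11).

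**Conclusion.** The point holds as a recommended design improvement. As written, the plan implies, and does not prevent, delivery of the shared feedback by a coordinator who has just seen the allocation, with no full script, fidelity check or blinding. The consequence is a possible bias of unknown direction in the exploratory between-arm difference. No differential delivery has been shown, and the documents do not allow the bias to be sized. The sample sizes in the sensitivity table show only how strongly later planning depends on this estimate. The conclusion rests on reading Sections 6 and 11 in their natural order and on feedback being a conversation whose tone, length and emphasis can vary within the fixed themes.

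**What to change.** Rewrite the Aim 2 sequence in Sections 6 and 11, identically for both sites:

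1. Consent.
2. Baseline measures, including the depression screen.
3. Feedback to every remaining participant, with completion time-stamped in REDCap.
4. Only then open the randomization website, and register intervention participants with Bottle Cap.

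State that allocation may not be opened until the feedback time-stamp exists. Randomization runs in a separate web application, so the time-stamp documents the order but does not enforce it; compare the two times during routine monitoring. Keep block sizes undisclosed to coordinators, or vary them.

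The cost is small: a wording change through both IRBs and one REDCap field. The 69 recruited and roughly 60 analysed per arm, and the 294 and 346 for a later trial, are unchanged, and no visit or assessment is added. Anyone who leaves between feedback and randomization is not randomized; report how many do, and say whether they count as recruited for the feasibility endpoint. The documents do not give enrolment status. If enrolment has begun, record the date of the change, because feedback will have been given under two procedures. The reorder does nothing for staff-collected self-reported outcomes, which need separate attention.

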7. ELIGIBILITY CRITERIA

- *Describe the characteristics of the subject population, including their anticipated number, age, ranges, sex, ethnic background, and health status. Identify the criteria for inclusion or exclusion of any subpopulation.*
- *Explain the rationale for the involvement of special classes of subjects, such as fetuses, pregnant women, children, prisoners or other institutionalized individuals, or others who are likely to be vulnerable. You cannot include these populations in your research, unless you indicate such in the protocol*
- *Similarly, detail exclusionary criteria: age limits, special populations (minors, pregnant women, decisionally impaired), use of concomitant medications, subjects with other diseases, severity of illness, etc.*

Healthcare Workers (Aim 1)

Inclusion Criteria:

- 1) Employed as a physician or nurse
- 2) Currently treating head and neck cancer patients (surgically or with radiation)

Exclusion Criteria:

N/A

Patient Advisory Board (Aim 1) and Participants (Aim 2)

Inclusion Criteria:

- 1) Adult male or female patients 18 years or older
- 2) Diagnosed with primary cancer of: pharynx (nasopharynx, oropharynx, hypopharynx), larynx (all subsites), oral cavity (all subsites)
- 3) Having completed surgical, radiation, and/or chemotherapy treatment;
- 4) Post-treatment completion status of at least 3 months;
- 5) Able to communicate and read in English;
- 6) Possess a telephone with text messaging capability; and
- 7) Confirmation of alcohol consumption.

Exclusion Criteria:

- 1) Non-English speaker
- 2) Non-drinker
- 3) Previously enrolled in Aim 1 **(for Aim 2 only)**]
- 4) Clinically significant depression, as indicated by an assessment of ≥ 16 on the CES-D 11-item Iowa short form scale **(Aim 2 only)**

8. NUMBER OF SUBJECTS

- *Indicate the total number of subjects to be accrued locally. If applicable, distinguish between the number of subjects who are expected to be pre-screened, enrolled (consent obtained), randomized and complete the research procedures.*
- *If your study includes different cohorts, include the total number of subjects in each cohort.*
- *If this is multisite study, include total number of subjects across all sites.*

Aim 1

For this phase of the research, we will enroll until 15 PAB members and up to 5 healthcare workers complete Aim #1 research procedures at Northwell.

Aim 2

For this phase of the research, we will enroll until 69 HNC survivors to each of the study arms at Northwell Health (34 in the control arm and 35 in the intervention arm) complete Aim #2 research procedures, in order to contribute to the overall target accrual of 138 patients for the study (69 from Northwell, 69 from the VA). In the event that the VA is unable to enroll 69 HNC survivors to each of the study arms at their site, Northwell will enroll additional patients to ensure that we meet the overall target accrual for the study.]

9. STUDY TIMELINES

- *Describe the duration of an individuals participation in the study*
- *Describe the duration anticipated to enroll all study subjects*
- *The estimated date of study completion*

Aim 1

Aim 1 participants may be asked to attend 3-5 virtual or in-person interviews that may last up to 1 hours each. We anticipate we will conduct Aim 1 study activities for up to 6 months. The estimated date of completion of this aim is September 1, 2023.

Aim 2

For Aim 2, total study duration will be 6 months for all participants. All participants will be required to complete enrollment and baseline questionnaires and follow-up assessments at 3-months and 6-months post-enrollment, which will take 1 hour to complete. Participants randomized to receive tailored text messages will receive up to 3 messages, up to 3 times a week for the first 3 months of their participation in Aim 2. For all participants, study participation will be complete after the 6-month follow-up assessment. We estimate the date of completion of Aim 2 to be March 31, 2026.]

10. ENDPOINTS

- *Describe the primary and secondary study endpoints*
- *Describe any primary or secondary safety endpoints*

For Aim 1: Our main endpoint is a new library of text messages on Bottle Cap tailored to head and neck cancer survivors, both Civilian and Veterans.

For Aim 2: Our primary endpoint is alcohol cessation, a binary variable (drinking is occurring or drinking is not occurring) created based on data collected as part of the Time-Line Follow Back (TLFB) procedure and the alcohol use disorders identification test (AUDIT). While both TLFB and AUDIT will be used to collect data for this outcome, TLFB will supersede the AUDIT as the primary outcome measure if conflicting responses are provided. Feasibility of conducting a future large-scale efficacy RCT, defined as a recruitment rate of 70% (number of survivors recruited over approached) in the pilot RCT, will also be assessed as a primary endpoint. Our secondary endpoint is alcohol reduction which will be assessed as a percent change using the same methods described above for the primary endpoint (i.e., TLFB and AUDIT).

Our secondary outcomes are quality of life (measured with the Head and Neck Quality of Life instrument, a widely used 20-item Likert scale measure that evaluates quality of life related to eating, communication, pain, and emotion in the last 4 weeks), overall health (measured with the SF-12 Questionnaire), depression (measured with the Patient Health Questionnaire (PHQ-2)) with additional resources and linkage to care provided, social isolation (measured with the Lubben Social Network Scale) and loneliness (measured with the De Jong Gierveld Loneliness Scale). Additionally, during our Aim 2 pilot RCT, we will evaluate acceptability of the intervention, defined as a positive evaluation of the intervention as indicated by a mean value of 4 on a 5-point scale, with higher values = higher acceptability.

11. RESEARCH PROCEDURES

- *Include a detailed description of all procedures to be performed on the research subject and the schedule for each procedure.*
- *Include any screening procedures for eligibility and/or baseline diagnostic tests*
- *Include procedures being performed to monitor subjects for safety or minimize risks*
- *Include information about drug washout periods*
- *If drugs or biologics are being administered provide information on dosing and route of administration*
- *Clearly indicate which procedures are only being conducted for research purposes.*
- *If any specimens will be used for this research, explain whether they are being collected specifically for research purposes.*
- *Describe any source records that will be used to collect data about subjects*
- *Indicate the data to be collected, including long term follow-up*

Aim 1

The study team will work closely with the HNC patient advisory board (PAB) to participate in multiple interviews aimed to adapt an existing alcohol cessation messaging program (Bottle Cap) for HNC survivors based on the ORBIT model. If needed, the study team will screen the EMR for potential eligibility ((type of HNC, date(s) of treatment, age, sex, race, and education, etc.) to meet enrollment objectives. After consent is obtained, the study team will collect basic demographic information and may ask participants to participate in 3-5 interviews either in person or via tele or video conference. During these interviews, participants may be asked to give quantitative and qualitative feedback on a set of text messages (see attached document) that aim to help people to stop drinking alcohol based on their opinions regarding their efficacy. Interviews may be audio/visual recorded to ensure accuracy. Participant are informed of this in the consent document for Aim #1. Based on interview feedback, we will select the text messages that will be used in the Aim #2 intervention.

Participants will also be asked about their personal experiences in order to create new messages. Overall, we plan to adapt 50 messages in 3-5 rounds of adaptation sprints. All newly adapted messages will be incorporated into Bottle Cap's message library. We will submit a modification if the text messages differ significantly in content than those already created and submitted for review, or if the nature of the questions could change the risk/benefit ratio initially documented by the IRB.

Participants will be compensated up to \$125 for their participation in Aim 1; \$125 will be evenly divided among the total number of interviews needed to compensate participants for their involvement with each interview.

Aim 2

All participants will be initially screened via EMR records for potential eligibility (type of HNC, date(s) of treatment, age, sex, race, and education, etc.). A waiver of authorization for this access has been requested below. Study staff will seek permission to approach potential participants from the HNC survivor's provider before inviting the patient to extend an existing scheduled appointment to participate in the study. At the end of the clinic visit, the HNC survivor will meet with the study staff to obtain informed consent, schedule another time to discuss the study or obtain contact information to send the consent document (i.e., via REDCap or mail). After consent, the coordinator will record baseline data and all assessments. Participants that are found to have clinically significant depression (≥ 16 on the CES-D Iowa short form) will be withdrawn from the study and referred to social work.

Consented participants will then be block-randomized into one of 2 arms:

- i. **Control condition: Assessment and Feedback (AF).** Regardless of drinking level ascertained during the baseline questionnaires, the patient will receive feedback about their reported alcohol consumption from study coordinators (i.e. not through Bottle Cap). Feedback will be provided by study coordinators one time, in person or virtually (depending on how the participant elects to receive their baseline visit), after the baseline measures are completed, and include assessment of alcohol levels and recommending alcohol cessation. The feedback will emphasize that, according to leading medical associations, any consumption of alcohol is not advisable for cancer survivors, as continued

alcohol use is associated with a higher risk of cancer recurrence and reduced quality of life. A sample feedback statement is “one or two drinks might not seem much, but it can increase your chances of cancer recurrence”. Smoking cessation information will also be provided as per usual care. Patients will be urged to stop smoking and referred to a smoking cessation program if so desired. Participants will be asked to complete two follow-up questionnaires, one at 3 and one at 6 months post baseline, during scheduled follow-up visits. No further effort will be required.

- ii. **Intervention condition.** Survivors recruited from NWH who are randomized into the intervention condition will receive all research activities given in the control condition, plus the HNC-tailored alcohol cessation program. Study staff will register the survivor at the Bottle Cap website and confirm the person’s gender and age. Survivors will receive text messages three times a week, usually during the late afternoon/early evening period, when the risk of alcohol drinking is greatest, for a period of 3 months. Participants will be asked to complete two follow-up questionnaires, one at 3 and one at 6 months post baseline. As with the control condition arm, all study activities will end after 6 months.

All participants will receive up to \$100 compensation at the end of the study for their participation in Aim 2.

It should be noted that participants will have the option of completing all assessments electronically (i.e., via REDCap link), via hard copy (i.e., mailed form), and over the phone or in-person with the CRC/RA. In the event that participants opt to complete the questionnaire via mailed copy, over the phone or in-person, the CRC/RA will input participant responses into REDCap. For this study, all data collected will be coded and entered into REDCap (Research Electronic Data Capture), a vetted HIPAA compliant (Health Insurance Portability and Accountability Act) web-based application that manages research surveys and databases.

